- Subjects will be dosed with MDs twice daily (minimum 8 hours and maximum 16 hours apart with no more than 2 doses per calendar day). Lumicitabine may be given without regard to food.
- An electronic device will be provided to the parent(s)/caregiver(s) the investigator/study-site personnel will provide sufficient information to enable the parent(s)/caregiver(s) to complete the parent(s)/caregiver(s) eCOA. Parent(s)/caregiver(s) will complete the eCOA twice daily (in the morning and in the evening) until the Day 14 visit, and once daily (in the evening) up to the Day 28 visit, at approximately the same time each day. Whenever possible, the same parent(s)/caregiver(s) should complete the eCOA throughout the study.
- Clinical evaluation includes, but is not limited to, RSV disease symptoms, vital signs, oxygen requirement (type and duration), level of hospital care, duration of hospitalization, respiratory rate, body temperature, and SpO₂.
- A complete physical examination includes all body systems.
- A directed physical examination includes respiratory system, nose, ear, throat, facial and neck lymph nodes, and skin examination.
- A 12-lead ECG is strongly preferred but in cases where a 12-lead ECG is not possible or feasible, then a 6-lead ECG may be performed.
- Leftover blood samples and nasal swabs may be used for exploratory biomarker analyses.
- Mid-turbinate nasal swabs (from the same nostril throughout the study) to assess RSV viral load and resistance should be taken by parent(s)/caregiver(s) from Day 3 to Day 6 and by a trained study team member on Day 7, Day 10, Day 14, and Day 28. Samples should be taken once daily at approximately the same time

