each day prior to study drug administration. In case of nostril bleeding or irritation during the collection of a mid-turbinate nasal swab, all subsequent nasal swabs will be performed on the contralateral nostril. Should the study drug duration be increased to up to 10 days (following review of the data by the IDMC), samples will be taken every day at approximately the same time, up to and including 1 day (+2 days) following the last dose of study drug. The parent(s)/caregiver(s) should collect nasal swab specimens after being trained by the investigator/study-site personnel. The actual dates and times of nasal swab collection at home must be recorded in the eCOA by the parent(s)/caregiver(s). Nasal swabs collected at home should be stored immediately between 2°C and 8°C (in the refrigerator) and brought to the site at the next visit. Quantitative culture (plaque assay) will not be performed on samples collected at home but might be performed on samples collected at the hospital on Day 14 and/or Day 28 visit upon the request of the virologist.

- m. Only 1 blood sample will be collected if the biochemistry and hematology analyses are performed on the same day.
- n. A urinalysis will be performed on Day 7 if the subject is discharged before the sample on the last day of dosing can be collected.
- o. A random PK sample will be taken on Day 7. The actual dates and times of sample collection must be recorded in the eCRF.

ABBREVIATIONS

AE	adverse event
ALT	alanine aminotransferase
AUC	area under the plasma concentration-versus time curve
AUC _{0-24h}	area under the plasma concentration-versus time curve from time 0 to 24 hours after dosing
AUC _{0-last}	area under the plasma curve from time 0 to the time of the last quantifiable concentration
BCRP	breast cancer resistance protein
C _{12h}	predicted concentration at 12 hours post dose
C _{max}	maximum observed (or predicted) analyte concentration
CYP	cytochrome P450
DBP	diastolic blood pressure
DMID	Division of Microbiology and Infectious Diseases
DNA	deoxyribonucleic acid
EC ₉₀	90% of maximal effective concentration
ECG	electrocardiogram
eCOA	electronic clinical outcome assessment
eCRF	electronic case report form
eDC	electronic data capture
eGFR	estimated glomerular filtration rate
ER	emergency room
GCP	Good Clinical Practice
hMPV	human metapneumovirus
IB	Investigator's Brochure
ICF	informed consent form

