1.1. Trial Objectives

Primary Objective

The primary objective is to determine in hospitalized infants and children who are infected with Respiratory Syncytial Virus (RSV) the dose-response relationship of multiple regimens of lumicitabine on antiviral activity based on nasal RSV shedding using quantitative Real-time Reverse Transcriptase-Polymerase Chain Reaction (qRT-PCR).

Secondary Objectives

The secondary objectives are to determine in hospitalized infants and children who are infected with RSV:

- The safety and tolerability of lumicitabine.
- The PK of JNJ-63549109 in whole blood.
- The impact of lumicitabine on the clinical course of RSV infection.
- The impact of lumicitabine on the duration and severity of signs and symptoms of RSV infection as assessed by the Pediatric RSV Electronic Severity and Outcome Rating System (PRESORS) questionnaire completed by the clinician in the electronic clinical outcome assessment (eCOA) device.
- The impact of lumicitabine on the time to undetectable nasal RSV viral load.
- The impact of lumicitabine on the emergence of RSV strains with resistance-associated mutations.
- The relationship between the pharmacokinetic (PK) of JNJ-63549109 and the pharmacodynamic (PD) (antiviral activity, clinical symptoms, and selected safety parameters) after single loading dose (LD) and repeated oral maintenance dose (MD) of lumicitabine.
- The acceptability and palatability of the lumicitabine formulation.

Exploratory Objectives

The exploratory objectives are to evaluate in hospitalized infants and children who are infected with RSV:

- The relationship between viral load and clinical outcome, including the relationship between RSV RNA levels and:

- Requirement for and duration of supplemental oxygen.
 - Time to hospital discharge or readiness for hospital discharge, with readiness for discharge as evaluated by the investigator.
 - Time to clinical stability defined as the time from initiation of study treatment until the time at which the following criteria are met: return to pre-RSV infection status (hereafter referred to as “normalization”) of blood oxygen level (without additional requirement of supplemental oxygen compared with pre-RSV infection status), normalization of oral feeding, normalization of respiratory rate, and normalization of heart rate.

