5.2. Primary Efficacy Endpoint(s)

5.2.1. Definition

RSV RNA will be measured in mid-turbinate nasal swab specimens using an RSV-A/B qRT-PCR developed by DDL Diagnostic Laboratory.

The primary endpoint is RSV RNA \log_{10} viral load (measured by qRT-PCR in the mid-turbinate nasal swab specimens) area under the concentration-time curve (AUC) from immediately prior to first dose of study drug (baseline) until Day 7.

The primary estimates of the $AUC_{1-7 \text{ Days}}$ will be derived from a mixed model (see section 5.2.3 for the detailed specification). No imputations of missing data from nasal swabs post-baseline will be done in this model, as this mixed model would allow to make inferences under the missing at random assumption.

Note that for the primary endpoint the following rules apply:

- Only values as provided by the central lab will be used.
- Baseline is defined as the last measurement before first intake. In case a result is available that is no later than 1 hour after treatment initiation this may be used but only if no pre-treatment observation is available.
- For all post-baseline analysis visits the RSV RNA log₁₀ viral load result of the swab that was performed at that day will be used.
- In case multiple nasal swabs were taken on a single day the maximum on the log scale will be used as the value for that subject.

As a sensitivity analysis, descriptive statistics will be provided for the viral load AUC between 0h and 144h (AUC_{0-144h}); calculated by the trapezoidal summation rule, based on date time of sampling, including the timepoints with (imputed) values available:

$$AUC_{0-144h} = \frac{1}{2} \sum_{i=1}^n (y_i + y_{i-1}) \times (t_i - t_{i-1})$$

where $i=1,2,3,\dots,n$ are the time points when post baseline samples are collected, y_i is the log 10 viral load at the time and t_i is the time in hours post baseline. y_0 is the (imputed) log 10 viral load at baseline, t_0 is time 0 and t_n is time 144h.

The following additional rules, on top of the rules of the primary analysis, will be applied to deal with missing values before calculating the Viral load AUC_{0-144h}:

- The value at time point 0h, if not exactly at 0h, will be calculated based on intrapolation between the last observed pre-dose value and the first observed post-dose value.
- The value at 144h, if not exactly at 144h, will be calculated based on intrapolation between the last observed value before 144h and the first observed value after 144h.

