The *lower* option is selected as the contrast needs to have a value below zero (ie, there needs to be a reduction in $AUC_{1-7\text{Days}}$ comparing active treatment to placebo). In summary, a positive dose-response relationship will be concluded if based on this analysis for any of the two estimations the resulting adjusted p-value is lower than the associated Pocock critical value (see section 5.1.1).

The differences in the $AUC_{1-7\text{Days}}$ for active versus placebo will be derived using appropriate contrasts deriving least square mean differences, including the 95% 2-sided confidence intervals.

The individual $AUC_{0-144\text{h}}$ as calculated using the trapezoidal rule will be considered as a supportive analysis and will be analyzed using a linear model with $AUC_{0-144\text{h}}$ as a dependent variable and treatment group and stratum as fixed factors, and baseline \log_{10} viral load as fixed covariate. For this analysis no adjustments for multiplicity will be applied, that is the differences versus placebo will be estimated using appropriate contrasts with 95% confidence intervals.

Before unblinding, the viral load data will be evaluated to assess whether viral load measurements based on swabs performed by the Health Care Provider (HCP) are similar as the swabs not performed by a HCP. Individual line plots will be created to visually check individual patterns for any difference between the samples. Depending on the visual inspection a decision will be made if all samples or only the samples from swabs performed by a HCP will be considered for the primary analysis. For example, if for the majority of subjects there is a clear drop in viral load when switched from samples taken by a HCP and samples taken by a non-HCP, the decision could be that only samples from swabs done by a HCP will be used. This blinded data review will be done before the database lock of the interim analysis and may also take other data sources into account.

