5.3.1.3. RSV clinical outcome

Measurement	Formula
Length of hospital stay (hours) [Time-to event]	
The time from treatment initiation to hospital discharge (=event) in hours.
 
Subjects who complete or withdraw from the study prior to the event will be censored at the date of completion or withdrawal. If the time is not available they will be censored at 12:00. In case of death the subject will be censored at the maximum observed number of hours until the occurrence of the event or censoring for all subjects achieving the event or being censored because of study completion or withdrawal.
 
(Date and time of event or censoring - date and time of first dose of study drug)/3600, rounded to one decimal.

Time to readiness for discharge (hours) [Time-to event]	
The time from study treatment initiation to readiness for discharge (= event) in hours, with readiness for discharge defined by the investigator.
 
Derivation similar as “Length of hospital stay”

Length of hospital stay since hospital admission (hours) [Time-to event]	
The time from hospital admission to hospital discharge (= event) in hours.
 
Derivation of censoring similar as “Length of hospital stay”.
 
(Date and time of event or censoring - date and time of hospital admission)/3600, rounded to one decimal

Measurement	Formula
Time to readiness for discharge since hospital admission (hours) [Time-to event]	
The time from hospital admission to readiness for discharge (= event) in hours, with readiness for discharge defined by the investigator.
 
Derivation similar as “Length of hospital stay since hospital admission”

Duration of intensive care unit (ICU) stay (hours) [Duration]	
The total number of hours a subject stayed in ICU (= event) from first intake until study termination, calculated as sum of [(end date and time of event - start date and time of event)/3600], rounded to one decimal for all separate events per subject
 
If the initial start time is prior to the first dose of study drug, the duration prior to the first dose of study drug will be deducted from the overall duration.
 
If the end date is missing, the end date is considered to be after study completion or withdrawal. If the end date and time is after the study completion/discontinuation, the duration after the date and time of study completion/discontinuation will be deducted from the overall duration. If the time is not available it will be put at 12:00.

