Requirement for supplemental feeding/hydration	
Does the subject require supplemental feeding/hydration (e.g. IV catheter/nasogastric tube) after first dose of study drug?
 
Categories will be Yes (1) or No (0).
 
Only derive this parameter for subjects that didn't require supplemental feeding/hydration before first dose of study drug.

Time to end of intensive care	The time from first study drug intake until the time of

Measurement	Formula
unit (ICU) stay (hours) [Time-to event]	
discharge from the ICU after which the subject was not readmitted to the ICU (= event)
 
Subjects who complete or withdraw from the study prior to the event will be censored at the date of completion or withdrawal. If the time is not available they will be censored at 12:00. In case of death the subject will be censored at the maximum observed number of hours until the occurrence of the event or censoring for all subjects achieving the event or being censored because of study completion or withdrawal. If no admittance to the ICU was necessary, the value will be set to 0.
 
(Date and time of event or censoring - date and time of first dose of study drug)/3600, rounded to one decimal

Time to end of Oxygen supplementation (hours) [Time-to event]	
The time from first dose of study drug start of oxygen supplementation to the last end date and time of any oxygen supplementation (= event) in hours (Oxygen supplementation is indicated on the Oxygen Supplementation form: Type of supplemental oxygen administration.). (Note: it is not necessary that the subject started on oxygen at baseline.)
 
If the end date is missing, the end date is considered to be after study completion or withdrawal.
 
Subjects who complete or withdraw from the study prior to the event will be censored at the date of completion or withdrawal. If the time is not available they will be censored at 12:00. In case of death the subject will be censored at the maximum observed number of hours until the occurrence of the event or censoring for all subjects achieving the event or being censored because of study completion or withdrawal.
 
If no oxygen supplementation was necessary after first dose of study drug, the value will be set to 0 hours.
 
(Date and time of event or censoring - date and time of first dose of study drug)/3600, rounded to one decimal

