Additionally these time-to event parameters will be analyzed for all ITT-i subjects using Kaplan-Meier analysis as indicated above and using a stratified Gehan test to compare between treatment groups

Time to clinical stability and Time to return to pre-RSV disease level

These time-to event parameters will be analyzed as indicated above using Kaplan-Meier analysis.

The differences in time of active dose regimens versus placebo treatment will be estimated using a Cox proportional hazard model; as baseline covariates, stratification factors, absence/presence of other viral or bacterial infections, and baseline log₁₀ viral load will be added. Treatment effect versus placebo will be reported, including 95% confidence intervals. A Log-log plot of survival will be added to check the proportional hazard assumption.

Additionally, the time-to event data will be analyzed using the logrank test and Gehan-Wilcoxon method.

Incidence of acute otitis media and all-cause mortality

The incidence of acute otitis media and of all-cause mortality will be analyzed similarly. Note that these incidences are only analyzed if any subjects have acute otitis media or if any deaths occur.

The proportion of subjects with presence/absence of acute otitis media and who died yes/no will be shown in a frequency tabulation (with corresponding 95% CI) and per treatment group.

A stratified logistic regression model will be used to analyze the outcome.

Relationship between RSV RNA viral load and clinical outcome

The following relationships will be investigated:

RSV RNA log₁₀ viral load AUC_{0-144h} versus

- Requirement for oxygen supplementation
- Time to end of Oxygen supplementation

- Length of hospital stay
- Time to readiness for discharge
- Length of hospital stay since hospital admission
- Time to readiness for discharge since hospital admission
- Time to clinical stability
- Time to return to pre-RSV functional status

The definitions of these parameters can be found in sections [5.3.1](#).

A Tabulation of the requirement for oxygen supplementation will be presented by quartiles of viral load AUC_{0-144h} .

Kaplan-Meier analysis by quartiles of viral load AUC_{0-144h} will be done for the time to variables.

Relationship between RSV RNA viral load and signs and symptoms of RSV infection

The following relationships will be investigated:

Quartiles of viral load AUC_{0-144h} versus

- Severity of signs and symptoms of RSV infection as rated by the clinician.

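### AUC0-144h is related to discharge and oxygen times that can end inside the same 144 h, so direction is unreadable, and the move to home swabs at discharge can create a false link

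*SAP*

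**What the plan says.** The aim is an exploratory objective (SAP 1.1): "The relationship between viral load and clinical outcome, including the relationship between RSV RNA levels and" oxygen use, discharge or readiness for it, and clinical stability. SAP 5.3.2.3 plans "Kaplan-Meier analysis by quartiles of viral load" AUC0-144h for the time-to-event outcomes, a table of oxygen requirement by the same quartiles, and Spearman coefficients with scatterplots. SAP 5.4.2 repeats the quartile approach for symptom duration, which it equates with time to readiness for discharge. It uses an AUC over 0-7 days, a label the SAP does not define elsewhere.

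The exposure comes from SAP 5.2.1, where "descriptive statistics will be provided for the viral load AUC between 0h and 144h" by the trapezoidal rule. The outcomes are in SAP 5.3.1.3. Length of stay is "The time from treatment initiation to hospital discharge (=event) in hours". For end of oxygen, "If no oxygen supplementation was necessary after first dose of study drug, the value will be set to 0 hours". The since-admission versions start earlier. No landmark or time-dependent method is given.

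The Protocol's Time and Events Schedules allow discharge once Day 2 procedures are complete. In hospital, trained staff take the swabs, which are frozen as soon as possible. After discharge, swabs "should be taken by parent(s)/caregiver(s) from Day 3 to Day 6 and by a trained study team member on Day 7", and "Nasal swabs collected at home should be stored immediately between 2°C and 8°C (in the refrigerator) and brought to the site at the next visit".

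SAP 5.2.3 plans a blinded look at individual line plots to compare staff-taken (HCP) and other swabs. Its example of a trigger is "a clear drop in viral load when switched from samples taken by a HCP and samples taken by a non-HCP" in most subjects. The resulting choice, all swabs or HCP swabs only, is worded for the primary analysis.

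**The concern.** There are two separate problems.

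First, exposure and outcome share the same hours. For a child discharged soon after Day 2, most of the AUC is measured after the event. For a child with oxygen time 0 h, every post-baseline swab follows it. A lower AUC in early leavers could mean that viral load drives recovery, or only that recovery and viral decline proceed together. These displays cannot separate the two.

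Second, the outcome changes how the exposure is measured. Discharge switches both the person taking the swab and the storage. If home swabs read lower, early discharge lowers the AUC, which is the reverse of the relationship in the objective. A low-AUC quartile would then show shorter stays with no biological link behind it.

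At stake is how the trial's own analysis of viral load against clinical course can be read. The primary test, dose choice and stopping rules do not depend on it.

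**Working it through.** **The plan's own figures.** The documents give no expected result for this analysis. The one design figure that can be recomputed is the power. With 180 subjects at 1:1:1, SD 34% of the placebo AUC and 40% early onset, the average high-dose effect is 0.4 × 30 + 0.6 × 20 = 24%, and the low-dose effect is 0.8 × 24 = 19.2%. With Pocock-type spending and looks assumed at 90, 120 and 180 subjects, 10,000 simulations give 96.5%, against about 97% stated. The 34% is used below to set the spread of the AUC.

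**How much of the AUC can become home swabs.** AUC = ½ Σ (y_i + y_(i-1))(t_i − t_(i-1)). With seven daily swabs at 0 to 144 h, Days 1 and 7 each carry 12 h and Days 2 to 6 each carry 24 h. Days 3-6 carry 4 × 24 = 96 h, and 96/144 = 67%. A child discharged right after Day 2 therefore has up to two thirds of the AUC from caregiver swabs. A child in hospital to Day 7 has none.

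**Inputs assumed, not in the documents.** Baseline 6.0 log10, decline 0.55 log10 per day, within-child residual SD 0.5, log-normal stay with median 72 h and log-SD 0.5, viral load independent of stay, and home swabs lower by a fixed amount.

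- Average level over 0-144 h: 6.0 − 0.55 × 3 = 4.35 log10. Mean AUC: 4.35 × 144 = 626 log10·h.
- SD at 34%: 0.34 × 626 = 213 log10·h, or 0.34 × 4.35 = 1.48 log10 on the average level. Smaller baseline SDs understate the spread: 1.2/4.35 = 28% and 0.8/4.35 = 18%.
- Largest AUC loss for an early leaver at shifts of 0.5, 1.0 and 1.5 log10: 48, 96 and 144 log10·h, which is 0.23, 0.45 and 0.68 SD.

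**Results with no true link** (AUC variation near 34%, N 120-180; rejection at 0.05 serves as a gauge):

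| Home-swab shift | Q4−Q1 median stay | Spearman rejection |
|---|---|---|
| 0.5 log10 | about 7 h | about 9-14% |
| 1.0 log10 | about 14 h | about 33-46% |
| 1.5 log10 | about 20 h | about 60-79% |

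A quartile log-rank test, if one were run, would reject in 19-24% at 1.0 log10. With no shift it rejects in 5-7%, with a gap of about 0 h.

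**A second model** (log-SD of stay 0.6, median 72 to 144 h, N 120-180, home swabs proportionally lower) agrees in pattern. With no reduction, Spearman rejects in 4-5% and the Q4/Q1 ratio of median stay is 0.99-1.01. A 10% reduction gives 7-13% and 1.07-1.12. A 20% reduction gives 13-42% and 1.12-1.26. A 30% reduction gives 25-78% and 1.19-1.41.

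**Remedies tested.**

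- A 48 h landmark, with exposure from the Day 1-3 swabs, gives 5-8% log-rank rejection. It keeps Φ(ln(72/48)/0.5) = Φ(0.81) = 79% of children.
- Day 1-2 hospital swabs alone, at a 30% reduction and N = 120, give 5.7-5.8% (log-rank), 4.4-4.6% (Spearman) and a ratio of 1.00.
- HCP swabs only, with gaps interpolated, give Spearman 6-7% and a ratio of 0.94-0.98.

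**The case against.** Much of the opposing case stands.

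- A reader might infer that most discharges fall inside 144 h. The documents give no expected stay or oxygen duration. They show only that these events can fall inside the window.
- A reader might infer that overlap alone manufactures an association. It does not: with no swab difference, both models stay near the nominal level.
- A reader might infer that the SAP expects home swabs to read lower. It offers that only as a conditional example, and the size of any difference is unknown.
- No log-rank test by AUC quartile is specified; the SAP names that test for treatment comparisons. The Spearman step is called exploration, no test is attached to it, and it may be run within treatment groups. Smaller groups would lower the rejection rates without removing the bias.
- The HCP check could remove most of the artefact. SAP 5.2.1 builds AUC0-144h on top of the primary rules, so an HCP-only decision plausibly carries over, and a 1.0-1.5 log10 drop is more likely to be seen than 0.5.
- Replacing AUC0-144h with AUC0-48h would ask a different question and lose the early leavers.

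What remains is that the check is visual, has no threshold, looks for a drop in most subjects, and states its decision only for the primary analysis. A moderate shift could pass it. Even a clean check does not resolve direction.

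**Conclusion.** The point holds in a limited form. The AUC window runs alongside outcomes that can end within it, so these displays cannot show which way an association runs. Where home swabs differ systematically and the difference is not removed, discharge itself moves the AUC and a link can appear where none exists. Under the assumed 72 h median stay and 1.0 log10 shift, the false gap is about 14 h; at 0.5 log10 it is about 7 h, with rejection only modestly raised. These sizes rest on an assumed stay and an assumed shift; the 34% spread is the only calibrating figure from the documents. The swab switch acts directly on discharge outcomes and reaches the oxygen outcomes only through their correlation with discharge. A reader might go further and say that the planned result is bound to be spurious, or that the antiviral endpoint is compromised. The documents support neither reading, because the analysis is exploratory and the shift may be absent.

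**What to change.** Keep the AUC0-144h displays, labelled descriptive, and amend SAP 5.3.2.3 and 5.4.2 as follows.

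1. Add a landmark version for the time-to-event outcomes: AUC0-48h from the Day 1-3 swabs, clock starting at 48 h, restricted to children still hospitalised and event-free then, with the number of earlier events reported. Requiring both conditions keeps out caregiver Day 3 swabs from children already home but not yet clinically stable.
2. Add Kaplan-Meier curves by baseline viral load quartile in all ITT-i subjects, and the oxygen-requirement table by the same quartiles in those ITT-i subjects for whom that outcome is derived.
3. Repeat the AUC0-144h displays with HCP-taken swabs only, and state that the SAP 5.2.3 swab decision also governs these analyses. Define the 0-7 day AUC in 5.4.2 or replace it with AUC0-144h.

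The cost is some SAP wording and a few extra displays; study conduct and the primary test are untouched. The landmark version leaves out early dischargers, about 20% under the assumed stay, and is less precise. It therefore supplements the full-window display.

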The relationships described above will be explored by using the Spearman's rank correlation coefficients and scatterplots with smoother curve per treatment group.

The definitions of these parameters can be found in sections [5.3.2.1](#) and [5.4.1](#).

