5.4. Pediatric RSV Electronic Severity and Outcome Rating System (PRESORS)

5.4.1. Definition

Currently, no single outcome assessment tool is widely accepted to assess the severity of RSV in infants and children. Although various clinical scores have been developed for the evaluation of the severity of acute respiratory infections and/or bronchiolitis in infants and children, none have been sufficiently validated for the longitudinal monitoring of the severity of RSV infection. Considering that there are no widely accepted or fully validated clinical endpoints for use in studies of RSV treatment, the PRESORS, an electronic clinician and parent/caregiver RSV infection severity rating assessment, will be further developed and evaluated for validity and reliability in a phase 0 trials, 64041575RSV0001.

The PRESORS data may also be analyzed for specific psychometric properties outside the scope of this protocol (possibly in conjunction with data from study 64041575RSV0001). In that case results will also be reported separately.

This study includes the same version of the PRESORS as in this validation study. The scoring system that will be used during this validation is available in attachment 4.

The PRESORS scores are defined as in table below. These will be calculated at each scheduled time point a questionnaire was filled in. A change from baseline will also be calculated.

Domain	Items	Scoring
Severity of signs and symptoms during the past 12 hours as assessed by the Clinician	Attachment 4: Items 1-5 (Clinician)	Sum of the individual item scores. See appendix for item score.
Severity of signs and symptoms now as assessed by the Clinician	Attachment 4: Items 6-14 (Clinician)	Sum of the individual item score. See appendix for item score.
Study drug administration as assessed by the Clinician	Clinician's Items: Study drug administration	Number of reports, ranging from 0 (no reports) to 6.
Severity of signs and symptoms as assessed by the Caregiver	Attachment 4: Items 1-12 (Caregiver)	Sum of the individual item score. See appendix for item score.
Breaths/minute	Caregiver: Breaths/15s	4 times the Breaths per 15 seconds
Improvement during the past 12 hours as assessed by the Clinician	Attachment 4: Items 1-5 (Clinician)	Number of signs and symptoms that have decreased by at least 2 points during the past 12 hours as assessed by the Clinician per time point.

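### The SAP pairs clinician-rated severity with quartiles of viral load AUC, yet specifies Spearman correlations and smoothed scatterplots, which suit the continuous AUC0-144h already derived for each child

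*SAP*

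**What the plan says.** SAP 5.3.2.3 has two consecutive blocks on viral load.

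- **Clinical outcomes.** The first block sets log10 viral load AUC0-144h itself against eight clinical outcomes. It brings in quartiles only where grouping is needed: a table of oxygen requirement, and survival curves ("Kaplan-Meier analysis by quartiles of viral load AUC_{0-144h} will be done for the time to variables").
- **Signs and symptoms.** The second block has one entry. The x-variable is introduced as "Quartiles of viral load AUC_{0-144h} versus", and the outcome is "Severity of signs and symptoms of RSV infection as rated by the clinician". The next sentence says that the relationships listed before it are to be explored with Spearman's "rank correlation coefficients and scatterplots with smoother curve per treatment group".

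Two other places matter. SAP 5.2.3 shows that an individual AUC0-144h exists for each child: "as calculated using the trapezoidal rule will be considered as a supportive analysis". SAP 5.4.1 defines the clinician severity scores as totals: "Sum of the individual item scores. See appendix for item score". The outcome is therefore a many-level ordinal score and gives no reason to group AUC.

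The SAP specifies no analysis of clinician-rated severity against the continuous AUC. SAP 1.1 lists this relationship among the exploratory objectives.

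**The concern.** The stated x-variable and the stated methods do not fit each other. A rank correlation uses the ordering of all children. Once AUC is cut into four groups, children within a quartile are tied and their ordering is lost, which pulls the coefficient toward zero. A smoothed scatterplot is meant to show shape along a continuous axis. With four x-positions it amounts to four columns of points joined by a line.

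What is at stake is how well one exploratory relationship is described. SAP 5.4.1 says that no severity tool for RSV is widely accepted, so the size and shape of the link between viral load and clinician-rated severity are worth estimating as well as the data allow. A programmer following the text literally would correlate a four-level variable while the continuous one sits in the same dataset.

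**Working it through.** The plan gives no precision, power or sample size for this correlation, so there is no figure of its own to reproduce. The check asks what quartiling costs a Spearman coefficient.

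**Inputs from the documents**
- x as written: quartiles of AUC0-144h (SAP 5.3.2.3). x available: individual AUC0-144h by the trapezoidal rule (SAP 5.2.1 and 5.2.3).
- y: summed clinician item scores (SAP 5.4.1).
- Subjects: 60 planned per regimen (SAP 1.2.1); SAP 5.1.1 uses an expected final ITT-i size of 120, which is 120/3 = 40 per arm.

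**Assumptions not in the documents**
- AUC and severity approximately bivariate normal, with correlation 0.2 to 0.5.
- One severity value per child.
- A quarter of the children in each quartile.

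**Analytic check, for small correlations.** Let Z be the standard normal variable underlying AUC, and score the quartiles −1.5, −0.5, 0.5, 1.5 (variance 1.25).
- Correlation of quartile score with Z: 2 × [φ(0.6745) + 0.5 × φ(0)] / √1.25 = 2 × (0.3178 + 0.1995) / 1.1180 = 0.925. Squared: 0.856.
- Squared correlation of the full rank with Z: 3/π = 0.955.
- Relative efficiency, quartile against continuous Spearman: 0.856 / 0.955 = 0.897, a loss of about 10%.
- Ratio of the coefficients: √0.897 = 0.947, a shrinkage of about 5%.

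**Simulation, 10,000 replicates per cell.** With n from 40 to 180, correlation 0.2 to 0.5, and severity either continuous or rounded to an integer score, the squared ratio of mean coefficients lies between 0.896 and 0.911, a loss of 9% to 10%. At n = 60 and correlation 0.3, the mean Spearman coefficient is 0.284 with continuous AUC and 0.270 with quartiles.

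**Range by benchmark**
- On the pure rank scale, quartiles lose 1/16 = 6.25%.
- Against a Pearson correlation on normal data, they lose 1 − 0.856 = 14%.

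**In subjects, per treatment group.** 60 × 0.897 ≈ 54. With 40 per arm, 40 × 0.897 ≈ 36.

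**Where the quartiles are cut.** The SAP does not say whether cut-points are pooled or set within arm. With pooled cuts and the planning assumptions of SAP 1.4 (high-dose reduction of 30% or 20% by symptom onset, 40% early onset, low dose at 80% of that effect, SD 34% of placebo AUC), placebo children fall about 13/21/28/39% across the quartiles. Relative efficiency is then about 0.87 for placebo, 0.90 for low dose and 0.89 for high dose, a loss of 10% to 13%.

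**The case against.** **The wording may be a slip.** The method sentence refers to relationships in the plural, while the symptoms block lists one. It may therefore reach back to the clinical-outcome block, where the x-variable is AUC0-144h itself. A smoothed scatterplot normally implies a continuous axis, so the word quartiles may have carried over from the Kaplan-Meier line just above. This is plausible. It does not remove the point, because even on that reading the only x-variable written down for severity is the quartile.

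**The consequence is small.** This stands. The analysis is exploratory, and a 5% change in a descriptive coefficient is unlikely to alter anyone's interpretation.

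**Stronger readings a reader might infer, which the documents do not support**
- *That the trial loses power.* No test, significance level or hypothesis is attached to this correlation, and any power figure would depend on a correlation the documents do not give.
- *That about 18 of 180 children are in effect discarded.* The SAP asks for the display per treatment group, and its expected final ITT-i size is 120. A pooled analysis of 180 is not clearly planned.
- *That the estimate has a larger standard error.* In simulation at n = 60 the sampling SD is nearly the same for both versions (0.124 and 0.124 at correlation 0.20; 0.114 and 0.116 at 0.35). The loss comes from the smaller coefficient.
- *That quartiles show no pattern at all.* Four ordered groups can show a monotone or non-monotone trend, though little finer shape.

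**Real data will not be bivariate normal.** Negative PCR results are set to 0, a missing final value is carried forward, and the severity score is a bounded sum recorded at many visits, with no visit named for this correlation. This stands too, so the 10% is a guide only.

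**Conclusion.** The point holds as a small, free improvement. As written, SAP 5.3.2.3 applies methods for a continuous variable to a four-level one, while the continuous AUC0-144h is already available for each child. Under approximate bivariate normality the cost is about 5% of the Spearman coefficient and about 10% of its efficiency (about 6% to 14% by benchmark), plus a smoother that reveals little about shape. These sizes rest on the assumed joint distribution, one severity value per child and, in the main calculation, equal quartile groups. The analysis carries no planned test and feeds no decision, so the consequence is a slightly weaker description of one exploratory relationship.

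**What to change.** In the signs-and-symptoms entry of SAP 5.3.2.3, remove the reference to quartiles so that the Spearman correlations and smoothed scatterplots use continuous AUC0-144h. Keep quartiles for the tabulation of oxygen requirement and the Kaplan-Meier displays, where grouping is needed. The change needs no new data, derivation or alpha, and it makes the unstated choice of cut-points irrelevant to the correlation. It amounts to a short edit to one line.
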